3.2. Biomarkers

3.2.1. Change in Bone Maturation

Bone maturation will be calculated as bone age (BA) divided by chronological age (CA). BA will be determined by a central reader via X-ray according to the Greulich-Pyle method and reported in years and months. These results will be combined into a decimal value as: years +

months/12. CA will be determined based on the assessment date. A decimal value will be calculated as: age in years + (assessment date – date of birthday + 1) / 365.25.

Change in BM at each visit in the OLE period will be calculated using the formula below:

$$\text{Change in BM} = \frac{\text{BA at post-baseline visit} - \text{BA at baseline}}{\text{CA at post-baseline visit} - \text{CA at baseline}}$$

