#### 8.4.7 Auxology/Clinical Endpoints

- Annual HV in cm/year at each 12-month interval.

- Change in height SDS every 12 months (compared to the previous values).
- Change in bone maturation (BM) every 12 months, (compared to Week 52 BA (calculated as BA/CA) at completion of LT-OLE year 1 and to previous values from LT-OLE year 2 onwards).

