This SAP provides the detailed methodology for summary and statistical analyses of the OLE data collected in Study CP-4-006 (████████). This document may modify the plans outlined in the protocol; however, any major modifications of the primary endpoint definition or its analysis will also be reflected in a protocol amendment.

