2.1.1. Estimand(s)

The estimand of this study uses the treatment policy strategy and estimates the effect for all participants treated regardless of whether an intercurrent event occurs. Each of them includes the following four attributes:

- Population: All patients who entered OLE period and had at least one dose of somatropin;
- Variable:
 - Annualized height velocity (AHV) at each 12-month interval (cm/year)
 - Height standard deviation score (SDS) and change in height SDS;
 - Change in bone maturation (BM);
 - IGF-1 and IGF-1 SDS levels on day 4 (-1) after somatropin dosing across study visits;
 - IGFBP-3 levels and IGFBP-3 SDS on day 4 (-1) after somatropin dosing across study visits;
 - Pubertal status (according to Tanner stages);
 - For males that are 13 years and older: luteinizing hormone (LH), follicle-stimulating hormone (FSH) and testosterone;

- For females that are 12 years and older: LH, FSH and estradiol
- Intercurrent event: All data after an intercurrent event (discontinuation of treatment, discontinuation of study, etc.), if collected, will be included;
- Population-level summary: descriptive summary for absolute values at each visit and/or change from previous interval.

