3.4. Baseline Variables

Baseline is defined as the main period baseline for efficacy and biomarker assessment. Except the reference visit for AHV, is defined in Section 3.1 as the values at the previous 12 month in the OLE period.

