6.1. Efficacy Endpoint

6.1.1. Main Analysis

- Estimand strategy: Treatment policy strategy for AHV every 12 months, as well as for absolute value and change from baseline for each of the efficacy endpoints, including height SDS, IGF-1 and IGF-1 SDS, IGFBP-3 and IGFBP-3 SDS, BM, LH, FSH and testosterone or estradiol.
- Analysis set: FAS (defined in [Section 4](#)).
- Analysis methodology: change from baseline to OLE Year 1, Year 2, Year 3, etc., will be descriptively and graphically summarized.
- Intercurrent events: Data after study drug discontinuation will be included.
- Descriptive summary includes N, mean, SD, median, minimum, and maximum for absolute value. It can be presented by treatment group (originally randomized to somatropin, originally randomized to Genotropin®, and total), by ADA sub-groups including ADA status (positive or negative), ADA titers, and by visit.

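### As it reads in the available text, the extension SAP's change in bone maturation is a rate of bone-age advance, and its reference visit departs from the protocol without explanation

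*SAP*

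**What the plan says.** **Formula.** SAP 3.2.1 begins: "Bone maturation will be calculated as bone age (BA) divided by chronological age (CA"). It continues: "Change in BM at each visit in the OLE period will be calculated using the formula below". In the available text the formula has one fraction bar. Above it stands BA at the later visit minus BA at baseline. Below it stands "CA at post-baseline visit" minus CA at baseline.

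**Reference visit in the SAP.** SAP 3.4 states: "Baseline is defined as the main period baseline for efficacy and biomarker assessment". The only exemption is annualized height velocity. SAP 6.1.1 includes BM in its list and asks for "absolute value and change from baseline for each of the efficacy endpoints". SAP 2.1.1 names change in BM as a variable and gives the population-level summary for all its variables as "descriptive summary for absolute values at each visit and/or change from previous interval".

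**Reference visit in the protocol.** Section 8.4.7 asks for a yearly change in BM and sets its reference as follows: "compared to Week 52 BA (calculated as BA/CA) at completion of LT-OLE year 1 and to previous values from LT-OLE year 2 onwards". The synopsis (LT-OLE endpoints) and section 8.6.5 give the same rule.

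**Status of departures.** SAP 2 says: "This document may modify the plans outlined in the protocol". It promises a protocol amendment only for major changes to the primary endpoint.

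**The concern.** Two separate things look wrong.

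First, a change in BM should be 0 when BM does not change. A ratio of increments is not. It measures how fast bone age advances per year of age, and it stays positive even while BM falls, as long as bone age still advances. SAP 6.1.1 also reports absolute BM, so a reader who subtracts two tabulated BM values would not arrive at the tabulated change.

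Second, the SAP and the protocol measure the change from different visits. For children switched from Genotropin, a change from the main-study baseline includes the Genotropin year, although the extension is meant to describe somatrogon.

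What is at stake is whether the extension tables report the endpoint that the protocol names. A programmer who follows SAP 3.2.1 and 3.4 to the letter would produce something else.

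**Working it through.** The documents give no figure for change in BM, so there is none to reproduce. The check compares the candidate definitions on assumed bone-age paths.

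**Inputs.** BM = BA/CA is from SAP 3.2.1. The main-study baseline as reference is from SAP 3.4 and 6.1.1. Week 52, then the previous annual value, is from protocol 8.4.7. All BA and CA values are assumptions, chosen to satisfy inclusion criterion 3 (BA not above CA). The protocol prints no formula; its wording is read here as a difference of two BA/CA values.

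**Definitions**, with k = 0 (main baseline), 1 (Week 52), 2 (extension year 1), 3 (extension year 2):

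- P (protocol) = BM(k) − BM(k−1)
- S1 (SAP, single fraction) = [BA(k) − BA(0)] / [CA(k) − CA(0)]
- S2 (two subtracted fractions, SAP reference) = BM(k) − BM(0)

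**How S1 and S2 relate.** Since BA(k) = BA(0) + S1 × [CA(k) − CA(0)],

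S2 = {[CA(k) − CA(0)] / CA(k)} × [S1 − BM(0)].

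So BM rises only when S1 exceeds baseline BM. The no-change value of S1 is BM(0), not 0.

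**Assumed child, CA 7, 8, 9, 10 and BA 5.0 at baseline**, so BM(0) = 5/7 = 0.714. Results are for extension year 1 / year 2.

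| BA path | BM at the four points | P | S1 | S2 |
|---|---|---|---|---|
| +1.0 per year: 5, 6, 7, 8 | 0.7143, 0.7500, 0.7778, 0.8000 | +0.028 / +0.022 | 1.00 / 1.00 | +0.063 / +0.086 |
| BM flat, +0.714 per year | 0.7143 throughout | 0 / 0 | 0.71 / 0.71 | 0 / 0 |
| BM falling, +0.5 per year: 5, 5.5, 6, 6.5 | 0.7143, 0.6875, 0.6667, 0.6500 | −0.021 / −0.017 | +0.50 / +0.50 | −0.048 / −0.064 |

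Check of the identity, first row, year 1: (2/9) × (1.00 − 0.7143) = 0.0635, which equals 0.7778 − 0.7143.

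**Reference visit alone**, on the BA/CA difference scale. Second assumed child: CA 7.5, BA 5.5, BM 0.733. Values are for extension year 1 / year 3.

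| BA gain per year | From previous annual value | From main baseline |
|---|---|---|
| 0.8 | 0.006 / 0.004 | 0.014 / 0.023 |
| 1.0 | 0.025 / 0.017 | 0.056 / 0.093 |
| 1.2 | 0.043 / 0.029 | 0.098 / 0.162 |

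The reference also matters if the single fraction is kept. With yearly BA gains of 1.5, 1.2 and 1.0, the year 2 value is 3.7/3 = 1.233 from main baseline but 1.000 within that year.

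**Switched children.** The Genotropin year is 1 of 2 years at extension year 1, 1 of 3 at year 2 and 1 of 4 at year 3. Take the first child's baseline with BA 6.5 at Week 52 and 7.3 at extension year 1:

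- P = 7.3/9 − 6.5/8 = 0.8111 − 0.8125 = −0.001
- S2 = 0.8111 − 0.7143 = +0.097
- S1 = 2.3/2 = 1.15, against 0.8/1 = 0.80 within the extension

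SAP 3.2.1 records BA in years and months, so 7.3 is not a recordable value. With 7 years 4 months (7.333), BM is 0.8148, P is +0.002 and S2 is 0.8148 − 0.7143 = +0.100. The gap between P and S2 remains at about 0.098 in both cases.

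**The case against.** **The formula may be a PDF artefact.** The SAP's other stacked formula, for height velocity in 3.1.1, is visibly broken in the same text. BM is defined as BA/CA just before the formula, and the neighbouring changes (height SDS, IGF-1 SDS, IGFBP-3 SDS) are plain differences. All this suggests that two subtracted fractions may have been meant. Against it, the text shows a minus sign both above and below a single bar. The layout is undetermined, so this part is conditional.

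**The SAP is allowed to depart from the protocol.** This stands. SAP 3.1.2 makes the same move for height SDS, which protocol 8.4.7 compares with previous values, so a deliberate cumulative convention is plausible. What remains is a departure that the supplied text does not identify or explain. The list of summary tables in SAP Appendix 6 is redacted and cannot settle it.

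**Stronger readings the documents do not support.**

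- A reader might infer that the SAP flatly contradicts itself. The line in 2.1.1 is generic, covers many variables and says and/or. It adds ambiguity, not a firm contradiction.
- A reader might infer from the switched child that the two references give opposite signs. A P of −0.001 is smaller than one month of bone age, (1/12)/9 = 0.009, and its sign changes with rounding to whole months. Only the difference in size can be relied on.
- A reader might infer that the Genotropin year is hidden. SAP 6 and 6.1.1 present results by randomized arm, so it sits in a labelled group; only the total column pools it.

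**Low stakes.** SAP 5.1 rules out hypothesis tests in the extension, and absolute BM is reported as well, so the intended quantity can still be derived. This limits the weight of the point but does not make the definition right.

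**Conclusion.** The point holds in two parts of different strength.

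**Formula, conditional on the printed SAP showing a single fraction.** The quantity labelled change in BM is a rate of bone-age advance. It is 0.50 to 1.00 in the tabulated examples, where the true year 1 and year 2 changes in BA/CA from main baseline run from −0.064 to +0.086. It would not reconcile with absolute BM.

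**Reference visit, on either layout.** SAP 3.4 and 6.1.1 replace the protocol's annual change by a cumulative one without saying so. In the second assumed child this multiplies the reported change in BA/CA by a little over 2 at extension year 1 (0.056 against 0.025 at one bone-year per year) and by about 5.5 at year 3 (0.093 against 0.017).

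These sizes rest on assumed bone-age paths and on reading the protocol's endpoint as a difference of BA/CA values. The governing protocol version also needs confirming: the SAP's version table cites Amendment V5.0 of 2 May 2018, while the protocol supplied is Amendment 2 of 27 April 2018.

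This should be fixed before the extension tables are programmed. No hypothesis, alpha or power is affected. Confidence is medium because of the formula's layout.

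**What to change.** 1. Check the formula in the original SAP PDF, and confirm which protocol version governs.
2. In SAP 3.2.1, define change in BM as BA/CA at the visit minus BA/CA at the reference visit.
3. Report the protocol's annual change: Week 52 as reference for extension year 1, the previous annual value afterwards.
4. If the cumulative change from the main-study baseline is also wanted, keep it as an additional, labelled summary and declare it as a departure, with a reason. Record the same decision for height SDS.
5. If gain in BA over gain in CA is reported, call it a rate of bone-age advance and state its reference visit.
6. Align SAP 2.1.1, 3.2.1, 3.4 and 6.1.1 with these choices.

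The cost is SAP wording, table code and one extra descriptive table. No new data are needed, since BA and CA are already available at each annual assessment.

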3.2.2. IGF-1 (ng/mL) and IGF-1-SDS

IGF-1 levels and IGF-1 SDS will be measured and calculated on day 4 (-1) after somatrogon dosing across study visits in OLE at every scheduled visit in OLE period. Change in IGF-1 SDS at each visit will be calculated as the difference between the IGF-1 SDS values in the OLE period and the IGF-1 SDS at the main period baseline.

3.2.3. IGFBP-3 (ng/mL) and IGFBP-3-SDS

IGFBP-3 levels and IGFBP-3-SDS will be measured and calculated on day 4 (-1) after somatrogon dosing across study visits in OLE at every scheduled visit in OLE period. Change in IGFBP-3 SDS at each visit will be calculated as the difference between the IGFBP-3 SDS values in the OLE period and the IGFBP-3 SDS at the main period baseline.

3.3. Other Endpoint(s)

3.3.1. Additional Assessment

The annual assessment will also be conducted according to the protocol schedule, including bone age, pubertal status (Tanner stage as stage I to V), LH, FSH, as well as testosterone for boys 13 years and older or estradiol for girls 12 years and older at every 12 months in the OLE period.

3.4. Baseline Variables

Baseline is defined as the main period baseline for efficacy and biomarker assessment. Except the reference visit for AHV, is defined in Section 3.1 as the values at the previous 12 month in the OLE period.

3.5. Safety Endpoints

3.5.1. Adverse Events

The AE including time of the onset, severity, action/treatment and outcome of the AE resolution, related to somatrogon treatment or not, will be collected at each scheduled visit with the visit window specified in the Schedule of Activities in the protocol.

An AE is considered as a treatment-emergent adverse event (TEAE) if the event started on or after the first dose of somatrogon in the OLE period of the study. The AE reporting period

for this study will be defined as the duration from the first dose of somatrogan in the study until 28 calendar days following the final visit dose. AE with partial dates will be assessed using the available date information to determine treatment-emergent status; AEs with missing onset date/time will be considered as TEAE. AEs with missing resolve date/time will be considered as ongoing.

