## 7. SAFETY AND PHARMACOVIGILANCE

### 7.1 ADVERSE EVENT

An AE is any adverse change from the patient baseline condition, whether or not considered IP related. This includes any subjective signs, symptoms or diagnosis, clinical significant deviation from baseline laboratory values or vital signs, or worsening (more severe, more frequent or increased in duration during the IP treatment) of the concomitant disease present at baseline visit (after initiation of IP treatment). Stable chronic conditions that are present prior to study entry and do not worsen during the study will not be considered AEs. Disease-related AEs will be considered AEs only if they worsen beyond what would be expected in the normal progression of the disease. In all cases, the etiology should, as much as possible, be identified and the Sponsor notified.

An abnormal result of diagnostic procedures including abnormal laboratory or vital sign findings will be considered an AE if it:

- Results in patient's withdrawal by the investigator,
- Is associated with clinical signs or symptoms,
- Is considered by the physician to be of CS.

AEs reported by the patient or observed by the Investigator will be individually listed on an AE form in the eCRF as follows: the specific event or condition, whether the event was present pre-study, the dates and times of occurrence, duration, severity, relationship to study medication, specific counter measures and outcome.

The intensity or severity of the AE will be characterized as:

- Mild: Transient or mild discomfort; no limitation in activity; no medical intervention/therapy required.
- Moderate: Mild to moderate limitation in activity - some assistance may be needed; no or minimal medical intervention/therapy required.
- Severe: Marked limitation in activity, some assistance usually required; medical intervention/therapy required; hospitalization possible.

Effective Date: Date of final electronic approval

The investigator will document in his/her opinion the relationship of the AE to study treatment using the criteria outlined in Table 1.

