6.5.1. Adverse Events

TEAE will be summarized with counts and percentage for safety population (defined in [Section 4](#)). The number and percentage of subjects who experienced at least one TEAE as well as the number and percentage of subjects who experienced each specific system organ class (SOC) and preferred term (PT) will be summarized and sorted by descending order of overall incidence.

All AEs will be reported in a data listing.

For analysis purposes, all AEs will be classified to the appropriate MedDRA PT and SOC. For each subject, multiple events that map to the same PT will only be counted once for the PT, and multiple PTs within an SOC will only be counted once for that SOC to assess patient incidence of events by PT and SOC. The count and percentage of patients with each PT and SOC will be summarized for each treatment group. Relationship and severity of AEs will be summarized (count and % of patients, incidence rate based on person-year) for each treatment group. For these summaries, multiple occurrences of an event within a patient will be classified as a single observation with the strongest relationship and maximum severity ratings. In addition, frequency tables of all reported events with each associated relationship and severity will be presented. Serious adverse events (SAEs) will be classified by the investigator and will be summarized by treatment group, PT and SOC, as well as total patients exposed.

In addition to the SOC and PT defined in the live MedDRA version at the final reporting stage, the adverse event of special interest (AESI) will be also summarized using frequency and percentage.

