Appendix 2. Data Derivation Details

Appendix 2.1. Definition and Use of Visit Windows in Reporting

Annual ADA characterization will be performed based on the algorithm below using visit windows as applied to ADPC dataset.

Period	From	To
Main	Day 2 (main dosing +1)	Day 410
OLE Year 1	Day 2/OLE Baseline (OLE dosing +1)	Day 410 (OLE Month 12)
OLE Year 2	Day 411	Day 774
OLE Year 3	Day 775	Day 1138
OLE Year 4	Day 1139	Day 1502

The following table will provide the adverse events reporting period to a given study period.

Period	From	To	AE linking to study period
Main	On or post first Main dosing date/time (in exposure dataset)	Prior to the first OLE dosing date/time	If the new AE strictly starts between the start and end dates of a given period, it will be counted in that period.
OLE Year 1 (visit13 -16)	On or post first OLE dosing date/time (defined in exposure dataset)	Visit 16 end date; if Visit 16 is missing, then first OLE dosing date + 365	
OLE Year 2 (visit 17-20)	“OLE Year 1 To” date + 1	Visit 20 end date; if Visit 20 is missing, then “OLE Year 2 From” date + 365	
OLE Year 3 (visit 21-24)	“OLE Year 2 To” date + 1	Visit 24 end date; if Visit 24 is missing, then “OLE Year 3 From” date + 365	
OLE Year 4 (visit 25-28)	“OLE Year 3 To” date + 1	Visit 28 end date; if Visit 28 is missing, then “OLE Year 4 From” date + 365	

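### An adverse event that began in the main study and worsens on somatrogon in the extension stays out of the OLE TEAE incidence unless the site opens a new record

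*SAP*

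**What the plan says.** SAP 3.5.1 classes an AE as treatment-emergent "if the event started on or after the first dose of somatrogon in the OLE period". The same paragraph adds one default: "AEs with missing onset date/time will be considered as TEAE". Partial dates are resolved from whatever date information exists. Nothing is said about an event already present at the first OLE dose that later gets worse.

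The period table in SAP Appendix 2.1 follows the same logic: "If the new AE strictly starts between the start and end dates of a given period, it will be counted in that period". The main period in that table closes just before the first OLE dose.

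SAP 6.5.1 builds the incidence tables on this definition: "TEAE will be summarized with counts and percentage for safety population". In the relationship and severity summaries, several occurrences in one patient are "classified as a single observation with the strongest relationship and maximum severity ratings". It also states: "All AEs will be reported in a data listing".

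Protocol section 8.6.6, under LT-OLE, rests the safety assessment mainly on the frequency of treatment-emergent AEs and on the number of out-of-range laboratory values. The protocol does not define treatment-emergent.

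**The concern.** Children randomized to Genotropin receive somatrogon for the first time at the start of the extension. If an event they tolerated on daily growth hormone deteriorates after the switch, that is information about somatrogon. A rule based only on onset date cannot register it, because the date that decides the classification was fixed before the child received the drug.

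The omission works in one direction. Leaving out a worsening criterion can remove events from the OLE TEAE count but cannot add any. Children who continue somatrogon are affected in the same way if a main-study event worsens in the extension, although for them the drug is not new.

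**Working it through.** The plan gives no figure on this point, so there is nothing to reproduce. The check applies the SAP rules to a test case.

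**Test case.** A child on Genotropin has a mild headache recorded as an AE at Month 10. It is ongoing at the first OLE dose (Month 12) and becomes severe at Month 14 on somatrogon.

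1. *TEAE status (SAP 3.5.1).* Onset at Month 10 is before the first OLE dose, and the onset date is known, so the missing-date default does not apply. Not an OLE TEAE.
2. *Study period (SAP Appendix 2.1).* The start date lies in the main period, so the event is counted there.
3. *OLE TEAE incidence (SAP 6.5.1).* Not included. The maximum-severity rule does not bring it in: it sets the severity shown for an event but does not date a change in severity or move the event to another period.
4. *If a new record is opened at Month 14.* Its onset is after the first OLE dose, so it is an OLE TEAE in OLE Year 1. The result therefore depends on how the site records the worsening.
5. *Do the documents settle the recording?* Protocol 5.8.1 asks that AEs be followed until they resolve or stabilize, and protocol 7.1 lists dates, duration and severity for each event. Neither tells sites to open a new record when an ongoing AE worsens.

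One contrast is worth noting. An AE with no onset date counts as treatment-emergent by default, while a worsening known to have occurred after the switch does not count if it stays under its original record.

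**Size.** The number of omitted events among switchers would be N × p × q × r, where

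- N = switchers, at most about 110 (planned Genotropin arm, protocol 8.1), or 110 × 0.9 = 99 after the planned 10% dropout;
- p = share with an AE ongoing at the switch;
- q = share of those whose AE worsens;
- r = share of worsenings kept under the original record.

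The documents give none of p, q or r. Purely as an assumption, p of 10–30%, q of 5–20% and r = 1 give 99 × 0.10 × 0.05 = 0.5 to 99 × 0.30 × 0.20 = 5.9 children; with r = 0 the answer is zero. This shows scale only and carries no evidential weight.

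**The case against.** The strongest reply is that the loss depends on an undocumented recording convention. The eCRF completion instructions, the data management plan and the sponsor safety rulebook cited in SAP 6.5 are not among the documents. If any of them requires a new record on worsening, the start-date rule captures the event. This stands as a condition on the point. It does not remove it, because the SAP's explicit definition would still need to agree with that convention.

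Three stronger readings are tempting, and the documents do not support them.

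- *The worsening vanishes except from the listing.* SAP 6.5.1 also promises frequency tables of all reported events by relationship and severity, and SAE and special-interest summaries. SAP 6.4.2 tabulates discontinuations due to AEs. None of these is expressly limited to TEAEs.
- *The SAP contradicts protocol 7.1.* The protocol's worsening wording covers "worsening (more severe, more frequent or increased in duration during the IP treatment) of the concomitant disease present at baseline visit". That is pre-existing disease, not an AE that arose on Genotropin. For baseline disease, a first worsening after the switch can be a new AE with a post-switch onset and so be counted.
- *Mild injection-site reactions or mildly raised glucose are lost in the same way.* Protocol 5.8.2 makes a reaction an AE only when it is abnormal by listed criteria, and protocol 7.1 sets conditions before a laboratory value is an AE. A mild finding would often not be an AE before the switch, so a later severe one would be new and counted. SAP 6.5.2 also provides laboratory shift tables. Headache is the cleaner example.

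Two further limits are fair. LT-OLE exclusion criteria 22 and 24 should keep some of the most serious ongoing events from crossing the switch. And SAP 5.1 plans no hypothesis test in the extension, so no formal inference depends on the count.

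**Conclusion.** The point holds in a limited form. As written, SAP 3.5.1 and Appendix 2.1 keep an AE that began in the main study and worsened in the extension out of the OLE TEAE incidence, provided the worsening stays under the original record. This is the effect of a stated rule, and any error it causes lowers the OLE count. It concerns the TEAE incidence tables, not every safety output.

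The number of children affected cannot be determined from the documents. The conclusion rests on the wording of the rule and on the absence of any instruction to open a new record, not on an estimated frequency. Because the extension is descriptive and other outputs may show some of these events, the change should be made but is not critical to the plan.

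**What to change.** In SAP 3.5.1, define an OLE TEAE as an AE that starts on or after the first OLE dose of somatrogon, or that was ongoing at that dose and afterwards increased in severity or became serious. Keep the present default for missing onset dates.

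In Appendix 2.1, assign an event that qualifies by worsening to the OLE year in which it worsened. SAP 3.5.1 says AE severity is collected at each scheduled visit, so that information can date the change. Check that the sponsor's safety rulebook and the eCRF instructions agree with the new wording.

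The cost is a short SAP change and one extra programming condition. It is not purely editorial: where the database holds a single severity per event without a date of change, some events will need a site query. TEAE counts may rise slightly. No dose, visit or clinical rule is touched.
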